3.1 Primary Endpoints

- Changes in markers of vasodilation (eNOS, nNOS), neo-angiogenesis (VEGF, CD-31), and systemic markers of endothelial function (EPCs, SDF-1α, and SCF).

3.2 Secondary Endpoints (efficacy):

- Differences in Doppler ultrasound parameters (PSV and EDV) from baseline to 6 months post-therapy.
- Treatment satisfaction as assessed by EDITS questionnaire in all subjects.
- Incidence of Serious Adverse Events experienced up to 6 months post-therapy.

3.3 Exploratory Endpoints:

- Change in IIEF-EF score from baseline to 3 and 6 months post-therapy.
- Percentage of subjects that achieve minimal clinically important difference (MCID) in IIEF-EF from baseline to 3 and 6 months post-therapy.
- Percentage of subjects who either decrease or discontinue use of PDE5i after three months post-therapy

4. Study Location

The study will be funded by the CTSI pilot award (GR019191) and coordinated by the University of Miami (UM), Miller School of Medicine, Desai Sethi Urology Institute. All

study visits will take place in the Department of Urology clinics, (PAC: [name], University of Miami Miller School of medicine, Miami, FL. & Lennar: [name]) PRP preparation and SWT therapy administration will take place in the PAC andrology lab and clinic.

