****CONFIDENTIAL & PROPRIETARY****

List of Abbreviations and Definition of Terms

AE	Adverse Events
BPH	Benign Prostatic Hyperplasia
BRB	Biomedical Research Building
CNS	Central Nervous System
CRF	Case Report Form
CTCAE	Common Terminology Criteria for Adverse Events
eCRF	Electronic Case Report Form
ED	Erectile Dysfunction
EDITS	Erectile Dysfunction Inventory of Treatment Satisfaction
EDV	End Diastolic Velocity
GCP	Good Clinical Practice
HIPAA	Health Information Portability and Accountability Act
ICF	Informed Consent Form
ICH	International Conference of Harmonization
ICI	Intracavernosal Injection
IEC	Institutional Ethics Committee
IIEF	International Index of Erectile Function
IIEF-EF	Erectile Function Subdomain Score
IRB	Institutional Review Board
ISCI	Interdisciplinary Stem Cell Institute
MCID	Minimal Clinically Important Difference
mL	Milliliter
ng/dL	Nanograms Per Deciliter
PDE5i	Phosphodiesterase 5 inhibitor
PPP	Platelet Poor Plasma
PRFM	Platelet Rich Fibrin Matrix
PRP	Platelet Rich Plasma
PSV	Peak Systolic Velocity
RCT	Randomized Controlled Trial
SAE	Serious Adverse Events
SEP3	Sexual Encounter Profile
SOP	Standard Operating Procedure
SWT	Low-intensity Shockwave Therapy
TE-SAE	Treatment Emergent Serious Adverse Events
UM	University of Miami
VAS	Visual Analogue Pain Scale

Protocol Synopsis						
TITLE	COMBINING SHOCKWAVE THERAPY AND PLATELET RICH PLASMA FOR TREATING ERECTILE DYSFUNCTION IN DIABETIC MEN (COCKTAIL-DM)					
SPONSOR	Jniversity of Miami, Miller School of Medicine - Department of Urology					
PHASE OF STUDY	Phase I/II					
STUDY THERAPY	Autologous Platelet-Rich Plasma (PRP) + Low-intensity Shockwave Therapy (SWT)					
STUDY DESIGN	Single arm, Open Label, Pilot Trial					
ROUTE OF ADMINISTRATION	Intracavernosal Injection (PRP) + extracorporeal shockwave therapy (SWT)					
SUBJECT POPULATION	15 male subjects between the age of 30-80 with Mild or Mild-to-Moderate ED and controlled Diabetes Mellitus (DM)					
STUDY	Primary: To investigate biochemical markers of neo-angiogenesis in patients before and after PRP injection + SWT					
OBJECTIVES	Secondary: To study efficacy and incidence of adverse events and safety of PRP injection + SWT treatment in men with mild-moderate ED, as measured by IIEF.					
	15 men with Erectile Dysfunction (ED) of organic origin and Diabetes (Type 1 or Type 2), that meet all of the inclusion and none of the exclusion criteria, will be enrolled and will receive PRP+SWT.					

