INVESTIGATION PLAN	Autologous PRP injection + SWT therapy. All subjects in this group will receive 2 sessions of autologous PRP penile injection with 30 ± 7 day treatment interval. 5mL of PRP will be injected at each session. Additionally, patients will receive a total of 3600 shocks over a five-week period, starting at initial PRP injection.					
DURATION OF STUDY	7 months (1 month screening, 5 weeks of therapy sessions, 6 months of follow-up).					
DEFINITION OF ENDPOINTS	 Primary: Changes in markers of vasodilation (eNOS, nNOS), neo-angiogenesis (VEGF, CD-31), and systemic markers of endothelial function (EPCs, SDF-1α, and SCF). Secondary: Differences in Doppler ultrasound parameters (PSV and EDV) from baseline to 6 months post-therapy. Treatment satisfaction as assessed by EDITS questionnaire in all subjects. Incidence of Serious Adverse Events experienced up to 6 months post-therapy. 					
	 Exploratory: Change in IIEF-EF score from baseline to 3 and 6 months post-therapy. Percentage of subjects that achieve minimal clinically important difference (MCID) in IIEF-EF from baseline to 3 and 6 months post-therapy. Percentage of subjects who either decrease or discontinue use of PDE5i after three months post-therapy 					

Protocol Synopsis							
	1. Be Male						
	2. Be 30 to 80 years of age (inclusive).						
	3. Be able to provide written informed consent.						
INCLUSION	 Have a diagnosis of mild to moderate ED (12-21) or mild ED (22-25) based on IIEF-EF questionnaire score. 						
CRITERIA	 Have diagnosis of Diabetes Mellitus (Type 1 or Type 2), as documented by history of Hemoglobin A1C > 7% OR on medical therapy for Diabetes. 						
	6. Be in a stable relationship and have a minimum of 2 sexual attempts per month for at least one month prior to enrollment.						
	7. Agree to comply with all study related tests/procedures.						
	 Previous penile surgery of any kind (except circumcision and condyloma removal), such as penile lengthening, penile cancer surgery, penile plication, grafting. 						
	 Previous history of priapism, penile fracture, Peyronie's Disease, or penile curvature that negatively influences sexual activity, 						
	 Abnormal morning serum testosterone level defined as a value lower than 300 ng/dL (±5%). 						
	4. Psychogenic ED as determined by study investigator.						
EXCLUSION	5. Patients using ICI for management of ED						

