1.3 Energy-based treatments for erectile dysfunction

Shockwave therapy has been utilized by urologists for other ailments, such as treatment of kidney stones through a non-invasive manner. Interest in the use of low-intensity shockwave therapy for erectile dysfunction was augmented with success seen in preclinical models. The hypothesis for SWT's mechanistic actions is neo-angiogenesis, recruitment of progenitor cells and resident stem cells, improvement of microcirculation, vasodilation with subsequent increase in nitric oxide, decrease in fibrosis, and nerve regeneration. There have been 13 published clinical studies regarding use of SWT for ED. Multiple systematic reviews and meta-analyses have been performed for SWT for ED, and there is consensus that SWT shows promise in the treatment for ED.

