1.4 Combination Restorative Therapy for Erectile Dysfunction

The development of ED therapeutics that focus on neurovascular regeneration and repair strategies are of great importance. A large body of *pre-clinical* work has demonstrated the effect of SWT alone (monotherapy) on angiogenesis and progenitor / stem cell recruitment for ED [2, 3, 8-11]. PRP monotherapy importantly is also supported by well-defined mechanistic insights obtained from rigorously conducted animal studies [12-19]. All the previous studies in humans have evaluated either IIEF scores and / or penile Doppler ultrasound hemodynamic parameters, but there has not been evaluation of the treatment as a combination. The proposed mechanisms of both interventions would

suggest that the combination therapy would act in a synergistic manner, with superiority over monotherapy. Success of our proposed work could fundamentally change the standard of care for ED and substantially improve the quality of life for tens of millions of men.

2. Study Objectives

2.1 Primary Objective:

To investigate of the underlying mechanisms of PRP and SWT in men with mild-moderate ED and Diabetes.

Exploratory:

- Change in IIEF-EF score from baseline to 3 and 6 months post-therapy.
- Percentage of subjects that achieve minimal clinically important difference (MCID) in IIEF-EF from baseline to 3 and 6 months post-therapy.
- Percentage of subjects who either decrease or discontinue use of PDE5i after three months post-therapy

2.2 Secondary Objective:

To study the treatment safety and efficacy of PRP and SWT treatment in men with mildmoderate ED and Diabetes.

3. Study Endpoints

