6.4 Withdrawal Criteria

All subjects who either screen fails, is withdrawn from the study, or has completed all visits should be de-enrolled from the research database within 2 business days, in accordance with university policies (or respective institutional policy).

Subjects may be withdrawn from the study for any of the following reasons:

- a) A subject does not meet the eligibility criteria (the subject will be considered a screen failure).
- b) A subject withdraws consent.
- c) A subject expires during protocol participation from causes other than the study treatment (not due to adverse events).
- d) At the discretion of the principal investigator for issues of non-compliance, or other behavioral factors.

7. Procedures Involved

15 men with Erectile Dysfunction (ED) of organic origin, that meet all of the inclusion and none of the exclusion criteria, will be enrolled to receive PRP+SWT in an open-label fashion.

Autologous PRP injection + SWT therapy. All subjects in this group will receive 2 sessions of autologous PRP penile injection with 28 ± 2 day treatment interval. 5mL of PRP will be injected at each session. Additionally, patients will receive a total of 3600 shocks over a five-week period, starting at initial PRP injection.

7.1 Schedule of Events:

-

The events table for the conduct of this study is shown below:

Table1:

Schedule of Events		Screening			Follow Up				
Time Point		0-30 days	Week 0	Week 1	Week 2	Week 3	Week 4	Month 3	Month 6
Eve	nt	before randomization	Day 0	Day 7 ± 2	Day 14 ± 2	Day 21 ± 2	Day 28 ± 2	Day 90 ± 14	Day 180 ± 14
Infor	med Consent	x							
Dem	ographics	x							
Medi	cal History	x							
Phys	ical Exam	x							
Dopp	oler Ultrasound	x							X
aires	IIEF	x						X	x
tionna	EDITS							X	x
Ques	VAS		x	x	x	x	x		
Labo	ratory Tests*	x							
EPC	-CFUs	X						X	Х
Brac	hial FMD	X						Х	Х
PRP Injection			х				х		
Shockwave Therapy			Х	Х	Х	Х	Х		
Concomitant Medications/Therapy		x	x	х	х	x	x	x	x
Review Adverse Events			х	x	x	x	х	x	x

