- 7.2.10 Endothelial Progenitor Cell Colony Forming Units (EPC-CFUs): Peripheral blood samples will be collected from participants for isolation of EPCs using Ficoll-Paque density gradient. Plasma will be aliquoted and stored for future analysis. Five million cells will be seeded on 6-well Fibronectin-coated dishes (BD Biosciences) in CFU-Hill medium (Stem Cell Technologies, cat#05900)4 and incubated at 37°C in humidified 5% CO2. Non-adherent cells will be collected after 48 hours, and 1 million cells will be seeded on 24-well Fibronectin-coated dishes. On day 5, EPC-CFUs will be counted in 6 wells and the average will be obtained.
- **7.2.11** Brachial Artery Flow Mediated Dilation (FMD): FMD% is a non-clinical measure; it is a tool used specifically for research to obtain an understanding the functionality of the vascular endothelium. 2D ultrasound will be used to measure Flow Mediated

Diameter percent change (FMD%). All measurements of the brachial artery diameter and FMD% will be performed in the morning, in a quiet and dark room and at controlled ambient temperature. Subjects will fast overnight and refrain from consuming caffeine, nicotine, or other stimulants for at least 8 hours prior to ultrasound and should refrain from vigorous exercise for at least 4 hours prior to ultrasound. Subjects are permitted to drink water and take medications (except PDE5 inhibitors) as usual. The subject will rest for 10 minutes in the supine position prior to scan. The subject's right arm will be comfortably immobilized in an extending position, allowing for ultrasound scanning of the brachial artery 5–10 cm above the antecubital fossa. In each examination, recording of vessel images will be followed by inflation of a cuff to supra-systolic pressure (40 to 50 mmHg above systolic pressure) for 5 minutes. Then the cuff will be deflated, and the brachial artery diameter will be imaged and recorded for 3 minutes.

- **7.2.12** *Platelet-Rich Plasma (PRP) Injection*: Approximately 120mL of blood will be collected from participants for preparation of investigational product. Refer to Section 8 for description of Investigational Product (IP) preparation and administration.

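### Six of the seven primary markers, including both neo-angiogenesis markers, have no stated assay, specimen or visit, and the stated analysis cannot test within-subject change in any of them

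*Combined protocol and SAP*

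**What the plan says.** **Endpoint.** Section 3.1 lists as primary "Changes in markers of vasodilation (eNOS, nNOS), neo-angiogenesis (VEGF, CD-31), and systemic markers of endothelial function", the last group being EPCs, SDF-1α and SCF. The synopsis repeats the list. That makes seven markers, with no time point, order or composite. By contrast, the Doppler, serious adverse event, IIEF-EF and PDE5i endpoints in the same lists all carry a time point.

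**Objective.** The synopsis gives the primary objective as "To investigate biochemical markers of neo-angiogenesis in patients before and after PRP injection + SWT". Section 2.1 puts it more broadly: "To investigate of the underlying mechanisms of PRP and SWT in men with mild-moderate ED and Diabetes".

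**Measurement.** Section 7.2.10 describes the EPC assay from blood draw to readout: "On day 5, EPC-CFUs will be counted in 6 wells and the average will be obtained". Table 1 in section 7.1 schedules EPC-CFUs at screening, Month 3 and Month 6. Section 7.2.10 also says of the same draw: "Plasma will be aliquoted and stored for future analysis". Section 10.2 adds that specimens are banked for later testing and names no marker. The laboratory tests named in 7.2.9 and 7.3.1 include none of the seven, and the laboratory row of Table 1 is marked at screening only.

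**Analysis.** Section 12.1 names repeated-measures ANOVA or a t-test for continuous data, in order to compare a treatment with a control group, at a level of 0.05. It gives no multiplicity rule. The synopsis describes a single-arm, open-label pilot of 15 men.

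**The concern.** A primary endpoint should tell the laboratory what to measure, in which specimen and when, and tell the analyst which comparison is primary. For six of the seven markers the plan does neither. The gap falls on the part that matters most: section 3.1 assigns VEGF and CD-31 to neo-angiogenesis, the synopsis objective is about neo-angiogenesis, and neither marker has a stated measurement.

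The plan leaves open whether none, some or all of the six will be assayed later. If none are, one of seven primary markers is reported and neither of the two neo-angiogenesis markers. If some are, the choice of markers can be made after the samples, and perhaps other results, exist. In every case the choice between Month 3 and Month 6 is open. A report could then present a chosen marker or visit as the primary result, and the protocol would not show whether it was the planned one.

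Even EPC-CFU, which is fully described as a measurement, has no usable analysis, because the only comparison stated needs a control group.

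**Working it through.** **1. Each primary marker against the plan**

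| Marker | Class in 3.1 | Assay described | Specimen named | Visits scheduled |
|---|---|---|---|---|
| EPCs | systemic | yes (7.2.10) | peripheral blood | screening, Months 3 and 6 |
| SDF-1α | systemic | no | no | no |
| SCF | systemic | no | no | no |
| VEGF | neo-angiogenesis | no | no | no |
| CD-31 | neo-angiogenesis | no | no | no |
| eNOS | vasodilation | no | no | no |
| nNOS | vasodilation | no | no | no |

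The count is 1 of 7 primary markers, and 0 of 2 neo-angiogenesis markers, with a specified and scheduled measurement.

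**2. Could another entry fill the gap?**
- *Laboratory tests.* The footnote to the starred row of Table 1 is missing from the text available for this review. The row is marked at screening only, so it cannot supply a before/after change whatever the footnote says.
- *Stored plasma.* It is taken within the EPC-CFU procedure, so by implication it exists at all three visits. No marker is assigned to it. Section 3.1 calls only EPCs, SDF-1α and SCF systemic; nothing says that the other four are to be read in plasma, and no tissue collection is described.

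**3. Analysis.** The synopsis states one arm; section 12.1 states a comparison between two groups. The test as written cannot be run for any of the seven markers. Repeated-measures ANOVA and the t-test could each serve for change within subjects, but the plan does not say that they are used so.

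**4. Multiplicity (secondary).** The documents contain no power or error-rate calculation to reproduce; the only inferential figure is 0.05. Suppose all seven markers are assayed, each is tested once at two-sided 0.05, and none truly changes:
- independent tests: 1 − 0.95^7 = 1 − 0.698 = 0.302;
- any dependence: at most 7 × 0.05 = 0.35;
- simulated one-sample t-tests, n = 15, 40,000 replicates: 0.24 at correlation 0.5 and 0.12 at 0.9.

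If only three or four markers are assayed, independence gives 1 − 0.95^3 = 0.143 or 1 − 0.95^4 = 0.185. The documents give no correlations, so those are assumptions. Testing both follow-up visits would raise these figures.

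**5. What 15 men can show.** With 15 complete pairs, the half-width of a 95% CI for mean change is t(0.975, 14)/√15 = 2.145/3.873 = 0.55 SD of the change. The change detectable by a two-sided one-sample t-test at an assumed 80% power (noncentral t, level 0.05/k) is:

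| k markers | level per marker | detectable change (SD of change) |
|---|---|---|
| 1 | 0.0500 | 0.78 |
| 3 | 0.0167 | 0.93 |
| 4 | 0.0125 | 0.97 |
| 7 | 0.0071 | 1.05 |

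These are Bonferroni figures, and Holm is no stricter. They apply to the t-test only. A three-visit repeated-measures ANOVA at 0.05/7, with equal variances and independent visits, needs 0.94 SD if the full change is present at both follow-up visits and 1.09 SD if it builds linearly. So 1.05 SD is not a ceiling for that analysis.

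**The case against.** The strongest reply is that the specimens exist. Plasma is stored from the EPC-CFU draw, and a small academic pilot may reasonably settle its assays later. That stands in part: a specimen that might serve some markers is probably available at all three visits, which makes the repair cheap. It does not remove the gap, because the plan never links the plasma to a primary marker, and deferring a primary assay to an unspecified later analysis is what allows selection.

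A second reply is that adjustment for multiplicity is not needed in a 15-man pilot that claims no power. That largely stands. Estimation without adjustment is acceptable, and multiplicity alone would not require a change. But section 12.1 does set a significance level, so a claim of significance is foreseeable.

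A reader might also infer more than the documents support:
- *That VEGF and CD-31 will not be measured and the synopsis objective will fail.* The plan is silent on these assays; it does not exclude them. What is shown is that it does not provide for them.
- *That any marker result would be a selected one.* If none of the six is assayed, EPC-CFU stands alone; if all are, the list is the one in 3.1. Selection among markers arises only if some are assayed or reported. The visit is open in every case.
- *That the two primary objectives conflict.* Section 1.3 names neo-angiogenesis among the proposed mechanisms of shockwave therapy, together with "recruitment of progenitor cells and resident stem cells". The synopsis objective is a narrower form of section 2.1, and EPC-CFU bears on the broader one. Aligning them is mainly editorial.

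**Conclusion.** The concern holds as a gap in specification. Of seven primary markers, one has a described and scheduled assay. The other six, including both that section 3.1 assigns to neo-angiogenesis, have no stated assay, specimen or visit. The only stated analysis needs a control group that the design lacks, so no test of within-subject change is specified even for EPC-CFU. This should be corrected before any stored sample is assayed, because afterwards the choice can no longer be shown to be independent of the data.

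The conclusion about measurement and analysis rests on the text alone and needs no numerical assumption. The false-positive figures (about 30% if independent, 24% at correlation 0.5) hold only if all seven markers are assayed and tested once each without adjustment, and they are secondary. The documents do not support the reading that the neo-angiogenesis markers will certainly go unmeasured.

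**What to change.** Before any stored sample is assayed:

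1. List the markers that will be measured from specimens already scheduled, with the assay and visit for each. Move every marker without a suitable scheduled specimen out of the primary list. Do not assume that plasma serves eNOS, nNOS or CD-31.
2. Name the primary visit.
3. For these markers, replace the treatment-control comparison in 12.1 with within-subject change from screening. Report estimates with 95% CIs and make no significance claim; if significance is to be claimed, apply Holm across the retained primary markers.
4. Align the synopsis and section 2.1 objectives with the retained markers. If neither VEGF nor CD-31 is kept, the synopsis objective must be reworded.

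The cost is laboratory work for the retained markers, some loss of primary status, and redrafting. No new participant procedure is needed for markers read from the existing draws; keeping a marker that needs another specimen would require one to be scheduled. Estimation gives up any significance claim, with intervals of about ±0.55 SD of the change if all 15 men have paired data. Holm keeps the claim but raises the detectable change: for a t-test at an assumed 80% power with 15 complete pairs, from 0.78 SD for one marker up to 1.05 SD for seven under Bonferroni.

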4.1 Additional Study Sites

No additional study sites.

5. Study Population

15 males with ED of organic origin and diabetes. All patients will be regular PDE5i users/responders. Men with ED will be evaluated by IIEF-EF domain and eligible patients will be enrolled in this open label pilot study. Participants who do not meet eligibility criteria will be considered a screen failure and will not receive the study therapy.

5.1 Inclusion criteria:

In order to participate in this study, a patient must:

- 1) Be Male.
- 2) Be 30 to 80 years of age (inclusive).
- 3) Be able to provide written informed consent.
- 4) Have a diagnosis of mild to moderate ED (12-21) or mild ED (22-25) based on IIEF-EF questionnaire score.
- 5) Have diagnosis of Diabetes Mellitus (Type 1 or Type 2) as documented by history of hemoglobin A1C > 7% OR on medical therapy for Diabetes.
- 6) Be in a stable relationship and have a minimum of 2 sexual attempts per month for at least one month prior to enrollment.
- 7) Agree to comply with all study related tests/procedures.

5.2 Exclusion criteria:

In order to participate in this study, a patient must not have any of the following:

- 1) Previous penile surgery of any kind (except circumcision and condyloma removal), such as penile lengthening, penile cancer surgery, penile plication, grafting.
- 2) Previous history of priapism, penile fracture, Peyronie's Disease, or penile curvature that negatively influences sexual activity.
- 3) Abnormal morning serum testosterone level defined as a value lower than 300 ng/dL (±5%).
- 4) Psychogenic ED as determined by study investigator.
- 5) Patients using ICI for management of ED
- 6) Patients with generalized polyneuropathy, neurological conditions, or psychiatric disease (such as bipolar disorder or depression).
- 7) Have a serious comorbid illness or condition that, in the opinion of the investigator, may compromise the safety or compliance of the subject or preclude successful completion of the study.
- 8) History of consistent treatment failure with PDE5 inhibitors for therapy of ED.
- 9) Poorly controlled diabetes as indicated by Hemoglobin a1c > 7.5%.
- 10) Use of antiplatelet medication.

6. Identification and Enrollment of Subjects

6.1 Recruitment and Pre-screening

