- **7.2.13** *Shockwave Therapy (SWT)*: In the treatment group, patients randomized will receive 5 weekly sessions, in which 720 shocks of treatment energy will be applied in every session to each treated region (left and right corpora cavernosa and crura) for a total of 3,600 shocks. Refer to Section 8 for description of Investigational Product (IP) preparation and administration.
- **7.2.14** *Concomitant Medications:* Review of current use of prescription and over the counter (OTC) medications. Participants must discontinue use of PDE5i medications throughout the duration of the study.
- **7.2.15 Review Adverse Events:** Refer to Section 11 for description and reporting of adverse and serious adverse events

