7.3.3 Follow Up Visits: Months 3 and 6 Post-Treatment

Follow up visits will occur within 90 \pm 14 days (Month 3) and 180 \pm 14 days (Month 6) days after final treatment visit. Refer to table 1 for procedures to be performed at the follow up visits visit.

8. Investigational Product

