It is the Investigator's responsibility to ensure that, prior to initiating this study, this protocol is reviewed and approved by the appropriate local and/or external IRB. The composition and conduct of this committee must conform to the United States CFR. The IRB/IEC must also review and approve the site's informed consent form (ICF), other written information provided to the subject.

If it is necessary to amend the protocol or the ICF during the study, the Sponsor-Investigator will be responsible for ensuring that the IRB/IEC reviews and approves these amended documents. An IRB/IEC approval of the amended protocol and/or ICF must be obtained in writing before implementation of the amended procedures and before new subjects are consented to participate in the study using the amended version of the ICF.

15.3 Conflict of Interest

Any investigator who has a conflict of interest with the study must have the conflict reviewed by a properly constituted Conflict of Interest Committee with the Committee-sanctioned conflict management plan that has been reviewed and approved by the study sponsor prior to participation in this study. All investigators will follow the University of Miami's (or applicable institution's) conflict of interest policy.

16. Publications

The preparation and submission of manuscripts for publication that contain results from this study shall comply with all applicable privacy laws and in accordance with processes determined by the University of Miami, Miller School of Medicine.

17. References

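### The exploratory endpoint on PDE5i reduction is assessed while PDE5i is banned, so it mainly measures adherence to the ban and cannot be read as efficacy

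*Combined protocol and SAP*

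**What the plan says.** The endpoint appears in the synopsis, under 2.1 and in 3.3: "Percentage of subjects who either decrease or discontinue use of PDE5i after three months post-therapy". The plan gives no reference time for the change and does not say whether a decrease means dose, frequency or both.

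Section 7.2.14 on concomitant medications sets the rule: "Participants must discontinue use of PDE5i medications throughout the duration of the study". The synopsis gives the duration of the study as "7 months (1 month screening, 5 weeks of therapy sessions, 6 months of follow-up", so follow-up lies within it. Section 7.3.3 is headed "Follow Up Visits: Months 3 and 6 Post-Treatment", and those are the only visits after treatment. No section ends the ban, allows rescue use or limits the ban to the treatment period.

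On use before the study, Section 5 says "All patients will be regular PDE5i users/responders". The inclusion criteria in 5.1 do not require PDE5i use. The data source is the "Concomitant Medications/Therapy" row of the schedule in 7.1, marked at screening, Weeks 0 to 4, Month 3 and Month 6. Section 7.2.14 describes it only as "Review of current use of prescription and over the counter (OTC) medications".

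**The concern.** The endpoint and the rule cannot both work as intended. Men described as regular users are told to stop, and are then counted as successes for having stopped. A man who gained nothing but obeys counts the same as a man who recovered and no longer wants the drug. A man who resumes may lack benefit, but he has also broken 7.2.14. The trial has a single arm, so there is no comparison group in which to see what the instruction alone produces.

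At stake is the reading of the result. A figure near 100% could be presented as freedom from PDE5i after therapy, and could be carried into the planning of a later trial, when it reflects an instruction.

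**Working it through.** The plan states no expected rate, power or target for this endpoint, so there is no figure to reproduce. The check is a reading of the text followed by simple arithmetic.

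**Inputs from the documents**
- Sample size: 15 (Section 5).
- Use before the study: all men are users (Section 5), though 5.1 does not require it.
- Ban: for the whole study (7.2.14), with follow-up included in the duration (synopsis).
- Post-treatment assessments: Month 3 and Month 6 only (7.1, 7.3.3).
- Design: single arm, open label (synopsis).

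**Step 1: timing.** The phrase about three months could mean the Month 3 visit or the period from Month 3 to Month 6. Both lie inside the study, so the ban covers the endpoint under either reading.

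**Step 2: full compliance, screening as the reference.** Screening is the natural reference because medications are first reviewed there; the plan does not say so. Let u be the number of enrolled non-users, with no dropout. A non-user has nothing to reduce, so

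rate = (15 − u)/15.

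| u | Rate |
|---|---|
| 0 (as Section 5 states) | 15/15 = 100% |
| 1 | 14/15 = 93.3% |
| 2 | 13/15 = 86.7% |
| 3 | 12/15 = 80.0% |

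The values u = 1 to 3 are an assumed range. Among users only, the rate is (15 − u)/(15 − u) = 100%. Treatment effect does not appear in either formula. Each user who goes back to his earlier level lowers the rate by 1/15 = 6.7 percentage points.

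**Step 3: full compliance, a later reference.** If the change is taken from a point when the ban already applies, a compliant man has no use left to reduce and the rate is 0%. The number differs, but it is again fixed by the rule.

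**Step 4: incomplete adherence, no treatment effect.** Take all 15 men as users. Let q be adherence to the ban and s the chance that a non-adherent man still reduces his use for other reasons. Both are assumptions. Then

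rate = q + (1 − q)s.

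| q | Rate at s = 0 | Expected count of 15 | P(at least 12 of 15), s = 0 | Rate at s = 0.2 |
|---|---|---|---|---|
| 1.0 | 100% | 15 | 1 | 100% |
| 0.9 | 90% | 13.5 | 0.944 | 92% |
| 0.8 | 80% | 12 | 0.648 | 84% |
| 0.7 | 70% | 10.5 | 0.297 | 76% |
| 0.5 | 50% | 7.5 | 0.018 | 60% |

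A useless therapy with 90% adherence would thus show at least 12 successes in 15 about 94% of the time. Adherence sets the floor of the result. Among users, a treatment effect can act directly only on the share 1 − q who break the ban. It may also influence q itself, because men without benefit are more likely to resume, but a single arm cannot separate that from ordinary adherence.

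**The case against.** **The plan may have foreseen PDE5i use.** Section 7.2.11 tells men to take their usual medications before the flow-mediated dilation scan apart from PDE5 inhibitors. Under a study-long ban that exception is not needed at Months 3 and 6. This is a fair sign of mixed intent. But the scan is also done at screening, when men may still be taking the drug, so the wording is compatible with the ban, and it does not lift it.

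**The ban may be the faulty side.** The endpoint appears three times and the ban once. Section 7.2.13 and parts of 7.3 and 8 also speak of randomisation or a control arm, which this trial does not have, so Section 7 may hold text that does not belong to this design. The documents cannot settle what was meant, and the sponsor may choose to end the ban instead. The conflict needs resolving either way.

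**The replacement carries the same mixture.** Counting men who resume is close to the complement of counting men who stop, and it also mixes adherence with lack of benefit. That is correct. The gain is that the figure is labelled as what it is and is not offered as a sign of benefit.

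**The figures rest on assumptions, and the endpoint is only exploratory.** Full compliance and the screening reference are assumed, and the non-user range departs from Section 5. The conclusion does not depend on that range, since u = 0 gives 100% and a later reference gives 0%. Some indirect information on efficacy does remain when adherence is imperfect. The exploratory status limits the harm but does not make the endpoint interpretable.

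**Conclusion.** The concern holds. Followed exactly, the plan fixes the result by rule: 100% of screening users when use at screening is the reference, or nothing left to reduce when the reference is later. When adherence is incomplete, the result mainly measures adherence, and any efficacy signal cannot be separated from protocol deviation.

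This rests on two readings: that the ban runs through follow-up, as the synopsis and 7.2.14 together say, and that no unstated exception exists. The 100% figure further assumes full compliance, no dropout and 15 users.

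The consequence is confined to one of three exploratory endpoints. No decision rule depends on it. It should be corrected because, as written, the endpoint cannot show what its wording implies.

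**What to change.** Keep the ban, since it keeps PDE5i from affecting the IIEF, flow-mediated dilation and Doppler results. Remove the bullet from the synopsis, 2.1 and 3.3, and replace it with a descriptive report: *number and percentage of men using PDE5i at screening who resume any PDE5i by Month 3 and by Month 6, reported as protocol deviation or rescue use.* Restricting the denominator to screening users also deals with any non-users enrolled. Because the protocol does not define rescue use, add one sentence saying what counts as such.

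If the sponsor wants PDE5i use as an outcome, the alternative is to end the ban at a stated time, define a decrease in dose or frequency, and measure change against use recorded at screening. That is a larger choice, because PDE5i permitted during follow-up could affect the Month 6 IIEF, flow-mediated dilation and Doppler measurements.

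The recommended change costs one exploratory endpoint and a minor amendment. Section 15.2 applies: "An IRB/IEC approval of the amended protocol and/or ICF must be obtained in writing before implementation of the amended procedures". No new data collection is needed, because the medication review already takes place at screening, at every treatment visit and at both follow-up visits.
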